6.4 Study Completion and Documentation of Allergy Testing Results

After the skin testing and/or oral challenge is completed, the participants will be asked to complete the subject acceptability survey to get their opinion of the PCN testing procedures conducted during the study, their results, and the subject's confidence that they will be able to take PCN (B-lactam) drugs in the future.

The subjects will be provided written documentation of the PCN (B-lactam) allergy testing procedures performed including a description of the skin testing and oral challenge, and verification of their PCN allergy test results (negative, positive or referral to allergist for further testing), which they will be encouraged to share with their medical providers.

In addition, we will provide the local STD clinic with the results, and these can be inserted into the medical record, as appropriate.

Subjects who have higher-risk histories which preclude skin testing and direct oral challenge or have ambiguous or uninterpretable results will be provided with a referral to local allergy providers. Each research site will maintain a list of local allergy providers for referral.

There are no follow up visits required. Subjects will be given instructions to contact study staff in the unlikely event of complications.

Incentives for a participant's time, transportation, and other expenses will be provided according to local IRB approval. Study staff will provide incentives depending on what procedures from the study visit the participant completed.

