2.2.3 Oral Challenge Approaches

The approaches recommended in the increasingly used algorithms, in many cases, advise bypassing skin testing and going directly to an oral challenge in low-risk patients. Two recent studies evaluated the impact and safety of this approach.

Iammatteo²³ instituted a direct oral challenge procedure in drug allergy clinics at Montefiore Hospital in the Bronx, NY. This study enrolled subjects >7 years old with non-life-threatening reported reactions to PCN. The exclusions included bronchospasm, anaphylaxis, non-IgE syndromes such as Stevens Johnson, cutaneous and/or mucosal blisters, hypersensitivity vasculitis, nephritis, hepatitis or anemia. Of 165 patients screened, 159 were enrolled and 156 completed a graded challenge without skin testing but which also incorporated a placebo. Of those challenged, 19 had reactions of which only 4 were determined to be allergy mediated and all were mild. It should be noted that this study skipped skin testing entirely.

Macy instituted a large PCN allergy management protocol at Kaiser Permanente San Diego.³ Between January 2017-December 2018, 806 patients had a direct oral challenge (no skin testing). Of these patients, 2 (0.2%) had an acute reaction, 9 (1.1%) had a delayed reaction; all were managed on-site with oral antihistamines or IM epinephrine; there were no hospitalizations. An additional 23 subjects (2.9%) had subjective reactions, such as mild nausea or headache.

Similarly, Blumenthal²⁴ implemented a risk-based algorithm in a large Boston based health system, and in a small study, directly challenged 83 low-risk patients in an outpatient setting. Of these patients, 3.6% experienced an immediate reaction (hives and rash), all resolved with treatment. In a larger antimicrobial stewardship-oriented intervention²⁵ which was performed in 5 acute care hospitals in 2016-17, patients with prior B-lactam allergy histories were evaluated using an EMR-based decision support tool and allergist consultation. A test dose of the prescribed B-lactam was administered in 1,045 instances to 942 patients with allergy histories considered low-risk. 96% of these cases did not have skin tests. Forty (3.6%) of patients had hypersensitivity reactions, 14 of which occurred within an hour of dosing. All were minor and treated successfully. Reactions were most frequent with late generation cephalosporins.

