2.3 Potential Risks and Benefits

2.3.1 Potential Risks

The risks associated with participation in the study are small. PCN skin tests are generally safe for adults and children of all ages, including infants. In certain circumstances, though, skin tests are not recommended. Skin testing with limited reagents may not be advised if:

- There is a strong history of a severe allergic reaction, e.g., anaphylaxis, within the past 10 years.
- The subject is taking medication that could interfere with test results. Antihistamines are the drugs most commonly associated with suppression of the skin test response.
- The subject has certain skin conditions which interfere with test interpretation, such as diffuse eczema or psoriasis.

The most common side effect of skin testing is slightly swollen, red, itchy bumps (wheals). These wheals may be most noticeable during the test. In some people, though, an area of swelling, redness and itching may develop a few hours after the test and persist for as long as a couple of days. These reactions can be treated with antihistamines, steroids or both.

Rarely, allergy skin tests can produce a severe, immediate allergic reaction such as swelling of the throat, difficulty breathing, a fast heart rate, or low blood pressure. These reactions are

largely eliminated by doing a preliminary prick (puncture) skin test which is part of the standard of care. Uncommonly, these symptoms can require immediate medical treatment with epinephrine.

Similarly, in people who skin test negative and are given an oral amoxicillin challenge, on rare occasions there can be an immediate or rapid development (within 6 hours) of a mild allergic reaction. This may include pruritis, rash or hives. In the vast majority of cases, these can be effectively treated with antihistamines.

Rarely, an oral challenge in an individual who skin tests negative can produce IgE-associated symptoms which can include rash, urticaria, bronchoconstriction and anaphylaxis requiring emergency care. Study staff at each site will be trained in managing these signs and symptoms and response kits will be available on site. The risk of this is estimated to be no different than that of an individual who does not have an allergy history.

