8 STATISTICAL CONSIDERATIONS

8.1 Study Outcome Measures

8.1.1 Primary Outcome Measures

The following primary outcome measures will be used to address the primary study objectives:

- Algorithm / PCN (B-lactam) allergy history screening questionnaire performance in ambulatory STD populations, specifically the NPV of the algorithm on true PCN (B-lactam) allergy.
- In ambulatory STD patients who report a history of PCN (B lactam) allergy and who have low-risk histories, determine the prevalence of PCN reactivity validated either by skin test or by direct oral challenge.

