8.2 Sample Size Considerations

The sample size for this study was selected to have adequate study power to conclude a high NPV of the PCN (B-lactam) allergy history screening questionnaire in ruling out the presence of true PCN (B-lactam) allergy. To address the objective properly, we applied Steinberg's et al.³² approach to obtain the minimal sample size needed to achieve a lower 95% confidence bound for NPV that exceeds the NPV with a useless test at a fixed level of significance with a given study power. Based on this approach, the sample size calculation depends on the prevalence of PCN allergy in the population and among observed study participants and the sensitivity and specificity of the PCN allergy diagnostic kit (PRE-PEN®). To target at least 85% power at 5% of significant level, the listed sample sizes (see table) provide lower 95% confidence bounds for NPV under the following various assumptions:

- The true population prevalence with PCN allergy: 1%, 3%, 5%
- The observed % of PCN allergy in this study: 1%, 3%, 5%
- The PCN allergy diagnostic kit with sensitivity at least 85% and specificity 95%
- 5% of participants who report a PCN allergy history will have a high-risk allergy history and therefore will not proceed to skin testing.

Population prevalence of PCN allergy	Observed % of PCN allergy in study	Estimated NPV	The lower 95% confidence bound for NPV						
			99.0%	98.4%	97.9%	97.5%	97.3%	97.0%	95.0%
1%	1%	99.84%	1259	796	635	556	526	488	351
	3%	99.51%	420	265	212	185	175	163	117
	5%	99.18%	252	159	127	111	105	98	70
3%	1%	99.84%	8119	2964	1958	1559	1421	1259	759
	3%	99.51%	2707	988	653	520	474	420	253
	5%	99.18%	1624	593	392	312	284	252	152
5%	1%	99.84%	113000	9519	4770	3378	2950	2483	1259
	3%	99.51%	37547	3174	1590	1126	984	828	420

	5%	99.18%	22533	1905	954	676	590	497	252
--	----	--------	-------	------	-----	-----	-----	-----	-----

For example, with 3% PCN allergy prevalence in population and among observed study participants, the NPV for a useless test is 97%. A useful PCN (B-lactam) allergy history screening questionnaire should have the lower 95% confidence bound for NPV greater than 97%. Based on the list a minimum sample size of 988 subjects who reported to have PCN allergy history would provide an estimated NPV = 99.51% with 85% power to conclude that the NPV of the study allergy history screening questionnaire is least 98.4% at 5% significant level.

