3. STUDY OUTCOME MEASURES

3.1 Primary Outcome Measures

- Algorithm / PCN (B-lactam) allergy history screening questionnaire performance in ambulatory STD populations, specifically the negative predictive value (NPV) of the algorithm on true PCN (B-lactam) allergy.
- In ambulatory STD patients who report a history of PCN (B lactam) allergy and who have low-risk histories, determine the prevalence of PCN reactivity validated either by skin test or by direct oral challenge.

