7.7 Analysis of Adverse Events

The Treated population and the Per Protocol population will be used for adverse event (AE) analysis. AEs will be summarized by time of onset (within/over 24 hours of study drug/test administration), relatedness to the intervention group, seriousness, severity, whether treated, outcome, and duration by intervention group, study site and overall. Categorical variables, and

continuous variables that have been categorized at discrete levels, will be summarized by frequencies and percentages. Continuous variables will be summarized by means, standard deviations, medians, minima and maxima.

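### The NPV is claimed for true penicillin allergy, but challenge reactions are read for only 30 to 60 minutes after the 250 mg dose; it should be stated as NPV for immediate reactivity

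*Protocol*

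**What the plan says.** - **Outcome.** Protocol 8.1.1 (repeated from 3.2.1) names questionnaire performance, "specifically the NPV of the algorithm on true PCN (B-lactam) allergy". SAP 3.1 repeats it: "specifically the negative predictive value (NPV) of the algorithm on true PCN (B-lactam) allergy". Neither document defines *true* by mechanism or by time. The second primary outcome, prevalence, is already worded as reactivity validated by skin test or challenge.
- **Reading of the challenge.** Observation lasts 60±10 minutes after 250 mg in the PST group (Protocol 6.3.1), and 30±10 minutes after the 250 mg step in the DOC group (6.3.2). The result is then recorded as negative, positive or unevaluable (6.3.3).
- **Label given.** Subjects within limits at that point are told, without qualification, that they are not allergic (6.3.1, 6.3.3). Protocol 6.2.1 describes the observation hour more narrowly, as excluding an immediate reaction.
- **Afterwards.** "There are no follow up visits required" (6.4). Subjects may contact staff about complications or new symptoms (6.4, 7.1.3). No rule says what a late report does to a negative result.
- **Late adverse events.** SAP 7.7 still splits by onset: "AEs will be summarized by time of onset (within/over 24 hours of study drug/test administration".
- **What the protocol expects.** In 2.3.1, after a negative skin test, "there can be an immediate or rapid development (within 6 hours) of a mild allergic reaction". The higher-risk history list in 6.1.2.1 includes effects more than 24 hours after dosing. In the 806-patient direct-challenge series (2.2.3), "2 (0.2%) had an acute reaction, 9 (1.1%) had a delayed reaction". In the acute-care test-dose series, 40 patients reacted, "14 of which occurred within an hour of dosing".

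**The concern.** The conclusion is worded more broadly than the data behind it. A subject who reacts after leaving is recorded as a true negative unless they call, and no rule reclassifies them if they do. Any error from this source goes one way, toward a higher NPV. A larger sample does not reduce it, and no planned analysis addresses it. It also carries into the short questionnaire, whose 4-6 items are chosen for the highest NPV (Protocol 8.4.1, SAP 7.3).

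SAP 7.7 has a related weakness. After the challenge visit nobody asks about symptoms, so a low count of challenge events beyond 24 hours could be read as reassurance when it mainly reflects lack of collection.

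**Working it through.** **1. The plan's own figure.** Protocol 8.2 says "To target at least 85% power at 5% of significant level". Its worked example uses sensitivity (se) 85%, specificity (sp) 95%, prevalence p = 3% in the population and in the study, target bound L = 98.4%, and 5% high-risk and not tested.

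- NPV = sp(1−p)/[sp(1−p) + (1−se)p] = 0.9215/(0.9215 + 0.0045) = 99.51%, as stated.
- N = (z_α + z_power)² × [se/((1−se)p) + (1−sp)/(sp(1−p))] / {log[(1−L)/L] − log[(1−se)/sp] − logit(p)}² = 2.681² × 188.94 / 1.203² = 938.8 tested.
- 938.8/0.95 = 988, as stated.

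This uses a one-sided 5% level. The analysis intervals are two-sided exact (SAP 5 and 7.3), so two-sided bounds are used below.

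**2. Why missed reactions pass straight into the NPV.** Only low-risk subjects are tested, so NPV = 1 − (detected reactors / tested). Each missed reactor raises it by 1/n.

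**3. Illustration from the 806-patient series**, assuming that all 9 delayed reactions fell outside the window:

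| Reactions counted | NPV | Exact two-sided 95% CI |
|---|---|---|
| 2 acute | 804/806 = 99.75% | 99.11 to 99.97% |
| 2 acute + 9 delayed | 795/806 = 98.64% | 97.57 to 99.32% |

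The difference is 9/806 = 1.1 points, for challenge reactions only.

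**4. How firm is the late share?**

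- 806-patient series: 9/11 = 82% (exact 95% CI 48 to 98%).
- Acute-care series: 26/40 = 65% (48 to 79%).
- Pooled: 35/51 = 69%.
- If the 9 delayed reactions were in fact in-window: 26/51 = 51%.
- If, in addition, about 12 reactions from three other cited series are counted as immediate (3.6% of 83 ≈ 3, described as immediate; 4 allergy-mediated and 1.5% of 328 ≈ 5, timing not stated): 26/63 = 41%.

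**5. Effect on the two reference values, n = 939 tested.** The two-sided lower bound exceeds 98.4% with at most 7 reactors (98.47% at 7, 98.33% at 8). It exceeds 97% with at most 17.

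| Rate applied to all 939 | Expected reactors | P(bound > 98.4%) | P(bound > 97%) |
|---|---|---|---|
| 2/806 | 2.3 | 99.7% | >99.9% |
| 11/806 | 12.8 | 5.8% | 90% |

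**6. The same check with skin-test positives.** Half the sample is skin tested, and a skin positive counts as a reactor whatever happens later. With equal groups, an assumed skin-positive rate s and challenge rate c, the overall rate is 0.5s + 0.5(1−s)c + 0.5c. With c = 2/806:

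| s (assumed) | Overall rate | Expected reactors | P(bound > 98.4%) |
|---|---|---|---|
| 0% | 0.25% | 2.3 | 99.7% |
| 1% | 0.75% | 7.0 | 60% |
| 2% | 1.25% | 11.7 | 10% |
| 3% | 1.74% | 16.4 | 0.8% |

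At s = 2% or more the 98.4% bound is probably missed even with no late reactions counted. The 90% for the 97% value also needs s = 0. At s = 1% and c = 11/806 the overall rate is 1.86%, with 17.4 expected reactors, and P(at most 17) is about 52%.

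**The case against.** The best defence is that the target is immediate hypersensitivity. Protocol 4.1 selects low-risk criteria for it, 6.2.1 observes for an immediate reaction, and 2.1 describes confirmed allergy as IgE mediated. On that reading a late reactor is not a false negative and there is no bias. This stands as a plausible intent. However, the outcome, the analysis and the statement made to subjects are not limited in that way, and 6.1.2.1 treats late effects as allergy history.

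A reader might go further and infer four things that the documents do not support:

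- **That most reactions would be missed.** The 806-patient series does not define *delayed* and says all reactions were managed on-site. The 40-reaction series gave test doses of whichever B-lactam was prescribed, in acute-care hospitals, with late-generation cephalosporins the most frequent cause. The 83-patient series describes its reactions as immediate, and a randomized comparison with 30-minute observation saw none.
- **That follow-up alone decides the 98.4% target (99.7% against 5.8%).** That contrast ignores skin-test positives. Also, 98.4% is a planning bound. Protocol 8.2 sets usefulness at a bound above 97%, and SAP 7.3 has no pass/fail rule.
- **That unsolicited calls are the only source of late adverse events.** Subjects skin tested at one visit may return within 6 weeks for the challenge (Protocol 6.3.4), and Appendix A marks adverse event assessment at that visit.
- **That observed reactors can be corrected by dividing by a capture share of 18% (2/11) to 35% (14/40).** Those inputs are imprecise and transfer poorly, and the result is zero when no reactor is seen.

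**Conclusion.** The point holds as a mismatch between claim and measurement. Challenge reactions after the observation window are not systematically captured, and the primary NPV is not limited to that window. If true allergy includes non-immediate reactions, the NPV is biased upward; if it means immediate reactivity, the documents need only say so.

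The size cannot be fixed from the documents. The 1.1-point illustration assumes that all 9 delayed reactions fell outside the window, that the 806-patient rates transfer to this population, and that no late report is used. The cited late share runs from 41% to 82% depending on assumptions that cannot be checked here. This should be fixed because it changes what the trial may conclude. It does not show that the NPV will be materially wrong.

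**What to change.** 1. In Protocol 3.2.1, 8.1.1 and 8.4.1 and SAP 3.1 and 7.3, state the NPV outcome and its conclusion as NPV for immediate reactivity: a positive skin test, or a reaction to oral challenge within the stated observation period. Add the same window to the prevalence outcome. Give the window by group; Protocol 7.1.3 has a single 60-minute figure that must be reconciled with 6.3.2.
2. In SAP 7.7, report events with onset after the challenge visit as passively reported, without a rate. Skin-test events assessed at an in-person return visit can be shown separately.
3. Add a tipping-point table: how many unobserved late reactors among challenge negatives would bring the lower bound below 98.4% and below 97%. At n = 939 these are 8 − x and 18 − x for x observed reactors:

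| Observed reactors | Late reactors to fall below 98.4% | Late reactors to fall below 97% |
|---|---|---|
| 0 | 8 | 18 |
| 2 | 6 | 16 |
| 5 | 3 | 13 |
| 7 | 1 | 11 |

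4. Reconcile the unqualified statement to subjects in Protocol 6.3.1 and 6.3.3 with the immediate-reaction wording in 6.2.1.

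The cost is wording in both documents, one extra table and a narrower claim. No additional data collection is needed.

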6.5 Provider Feasibility Sub study

A key operational question is provider acceptability and feasibility of PCN allergy evaluation including the allergy history screening questionnaire, skin testing and oral challenge in busy ambulatory STD settings. We will administer a brief electronic survey to providers at each of the clinics before implementation of the study and again at study conclusion. Since these are short surveys, and focus exclusively on clinical practice characteristics, consent will be obtained using either on-line consent or through an oral consent process.

All clinic providers who complete the provider feasibility survey will undergo the following procedures:

- Electronic informed consent (on-line or oral) to participate in the sub study
- Self-administration of the provider feasibility survey as an eCRF both pre-study implementation and at the end of the study

Although pre/post evaluation data will be available in aggregate, all clinic-based providers will be assigned a 5-digit Provider ID number which will be used to compare responses for individual providers at the beginning and end of the study. We anticipate that among the 5 participating clinics, we should be able to generate 50-100 surveys from staff who were present at the beginning and at the end of study. We anticipate that the total number of respondents will be no more than 150.

6.6 Data Handling, Data Quality Control and Record Keeping

For this study the FHI 360 Center for Data Management (CDM) will be responsible for all issues relating to data collection (forms, tools, and systems), quality control, and management. FHI 360 Biostatistics will provide statistical support for this study.

A detailed data management (DM) plan will be written prior to study initiation. The following is a summary of the plan.

6.6.1 Data Collection

Data will be collected using CRFs that are specifically designed for this study. The data collected on the CRFs will be captured in a clinical data management system (CDMS), that meets the technical requirements described in 21CFR Part 11, GCP and HIPAA. The CDMS will be validated to ensure that it meets the scientific, regulatory, and logistical requirements of the study before it is used to capture data. Before using the CDMS, all study personnel will receive training on the system along with study specific training. After they are trained, users will be provided with individual system access rights.

Data will be collected at the study site by appropriately designated and trained personnel. All screened participants who meet eligibility requirements will be assigned a PN. CRFs must be completed for each eligible participant. For eligible participants who decide not to enroll, data for the reason they declined enrollment will be collected on a refuser survey CRF. No identifying information will be collected on participants who do not consent for enrollment. Most of the data will be collected using paper CRFs. However, the PCN (B-lactam) allergy history screening questionnaire for participants and the provider feasibility survey for clinicians will be eCRFs. Data for the eCRFs will be collected using iPads.

No names or personal identifying information will be collected on the CRFs. Data will be verified by the site and reviewed for consistency by CDM using both automated logical checks and

manual review. Each site investigator (SI) or designee is responsible for the accuracy of data entered on the CRFs and will sign a statement on the final form for each participant acknowledging the review of all CRFs for that participant and certifying that all information on them is complete and accurate.

The completed CRFs will be scanned and emailed to CDM.

Digital images of the skin testing results will be collected and stored in the CDMS.

6.6.2 Data Quality Control

CDM is responsible for the accuracy, quality, completeness and internal consistency of the data from this study. Data handling, including data quality control, will comply with international regulatory guidelines, including ICH GCP guidelines. Data management and control processes specific to this study, along with all steps and actions taken regarding data management and data quality control, will be described in the DM plan.

Paper CRFs received at FHI 360 will be processed and entered, then queried for completeness, consistency and the presence of mandatory values. Logical checks will be implemented to ensure data quality and accuracy. Any necessary data changes will be made in the clinical database, and data review and validation procedures will be repeated as needed. Discrepancies found will be queried.

Data corrections will be made through the CDMS. The system audit trail captures the reason for each change, the previous and new data values, date and time and the username of the staff person making the change.

The statistician will request data freezes for all interim and final reports. Thorough cleaning and closure of participant data will be performed at study close-out according to the DM plan. Prior to closure, all participant data will be complete or accounted for.

At the conclusion of the study, the CDMS and all other study data will be locked to prevent further changes. Locking the study data represents the acknowledgement that all data have been captured and confirmed as accurate.

